### **6.3.4. Analysis of HINT-N in FAS and PPS**

All analyses performed on the HINT-Q will be replicated on the HINT-N, with the score at post-implantation visits considered as the response. (refer to tables 13 and 14).

### **6.3.5. Measures of impedance in FAS and PPS**

The time course of electrodes impedance performed at each time points will be analyzed through a mixed model for repeated measures and contrasts of interest. (refer to table 15).

### 6.3.6. ECAP

Measures will be performed over time from Baseline to Month 12 and results downloaded into the eCRF. Due to the differences format of ECAP files downloaded (pdf, Excel file, pictures), it will not be possible to perform ECAP analysis. Nevertheless, all the downloaded files will be provided.

## 6.4. Safety analysis

Every tables will be presented on Safety Analysis Set.

The total number of events, the mean number of events per patient and the percentage of patients experiencing events will be presented per preferred term (table 16.2).

In addition, a table will provide the number and the percentage of patients with (table 16.1):

- at least one Adverse Event (AE)
- at least one Serious Adverse Event (SAE)
- at least one Adverse Event that led to discontinuation (DisAE): action taken of the AE ticked Discontinued permanently
- at least one Fatal Adverse Event: outcome of the AE ticked Death
- at least one complication
- at least one minor complication

A presentation of all AEs will be made according to System Organ Class (SOC) and Preferred Term (PT) from MedDRA classification.

A table should describe of device related vs not device related AEs, as well as study vs not study related AEs. (Table 16.2 and related figure)

Incidence rates will be summarized for each PT and SOC terms (refer to table 16.3) AEs will be presented in terms of patients (number and percentage) and in terms of events (number and mean number per patient experiencing the event at least once). For the latter, an event occurring at 2 distinct times during the treatment period will be counted twice for calculating the mean number of events per patient. For one patient, if two events are both coded to the same PT, the patient will be counted only once at the PT level.

The time to the first minor or major complications will be investigated through Kaplan Meier survival (event free) analysis and the graph of the estimated event free probability by the time will be presented.

Listing of SAEs and deaths (age, gender, time to AE, description of AE, outcome, discontinuation, relationship, severity, PT and SOC terms) will be presented (refer to table 16.4).

## 6.5. Site effects analysis

The site effect is partly confounded with the language effect. Consequently, the site effect will be investigated in English speaking patients. An analysis of variance using the change from baseline to M6 as the response and the site as covariate will be performed. If the site effect is significant, then the mean change from baseline to M6 is dependent upon the site. Regardless the p value of ANOVA a Forest plot presenting the mean change from baseline to M6 of each site along with the 95% confidence interval will be presented to verify whether there is just a quantitative difference across sites or a qualitative one (refer to table 12 and the related figure). In case of significant site effect and qualitative difference the site with the largest mean deviation from the overall mean change from baseline will be removed from the sample to estimate the overall mean change from baseline in the remaining sites.

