#### **3.6.2.4 Secondary analyses**

Claims for labeling will be based only on confirmatory results demonstrate through the primary analysis.

All secondary or sensitivity analyses are supportive estimates of effects related to the primary or secondary objectives.

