### **h) Handling of site effects**

The site effect is partly confounded with the language effect. Consequently the site effect will be investigated in English speaking patients. An analysis of variance using the change from baseline to M6 as the response and the site as covariate will be performed. If the site effect is significant, then the mean change from baseline to M6 is dependent upon the site. Regardless the p value of ANOVA a Forest plot presenting the mean change from baseline to M6 of each site along with the 95% confidence interval will be presented to verify whether there is just a quantitative difference across sites or a qualitative one. In case of significant site effect and qualitative difference the site with the largest mean deviation from the overall mean change from baseline will be removed from the sample to estimate the overall mean change from baseline in the remaining sites.

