## 1.2. Study Objectives

The primary objectives are:

- To demonstrate the improvement in the speech recognition, in quiet condition, after implantation of the Neuro CIS with respect to preoperative conditions.
- To evaluate the device safety profile and in particular the risk of complication.

Evaluation at 6 months compared to baseline will be used to determine the efficacy of the device.

The incidence rate of major complications at 12 months of device use will be estimated to evaluate the safety. Data from literature on similar devices FDA-approved will be used as state of the art.

The primary population will be composed of English-speaking subjects. In the efficacy assessment, a sub-population will be used as a primary set of patients because different languages is expected to influence the magnitude of the effect of the device. The objective is to assess in English speaking subjects the device performance at month 6 in quiet conditions compared to baseline (best-aided condition) using HINT-Q test-sentences presented at conversational level.

Hypothesis: the mean HINT-Q score obtained with the Neuro CIS after 6 months of device use in English speaking subjects is greater than the score at baseline.

$$\begin{aligned} H0: \mu_{M6} - \mu_0 &\leq 0 \text{ points} \\ H1: \mu_{M6} - \mu_0 &> 0 \text{ points} \end{aligned}$$

An improvement of approximately 50 points with respect to baseline is expected and an improvement of 20 points is considered clinically pertinent.

Occurrence of major complications in all participants suffering from severe to profound bilateral sensorineural hearing loss and for whom an implantation of the device was initiated will be the co-primary objective. All surgical and device-related events will be reported, and the number and proportion of major complications will be estimated.

Adverse events or complications will be classified as medical/surgical or device related. Complications will be classified as major if they require surgical intervention and minor if they resolve spontaneously or with non-invasive medical treatment categories. Any device failure will be investigated and classified according to AAMI CI86:2017 guideline for Cochlear Implants.

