## 6. Statistical analysis

### 6.1. Analysis of efficacy endpoint

The primary analysis of the primary efficacy endpoint will be performed on a subgroup of the FAS which consists of all English-speaking subjects.

Additional analysis with a replicate PPS will be performed on this subset of English-speaking patients.

The primary test is a one sample T-test performed on the change from baseline to 6 months after activation of the device. The value of the mean improvement under the null hypothesis is zero. The type I error ( $\alpha$ ) is set to 0.025 (one-sided).

The one sample Wilcoxon rank test will be applied in a sensitivity analysis. In case the normality assumption is strongly violated or in the presence of several outliers, the result of this sensitivity analysis will have a particular importance.

To further describe the benefit of the Neuro CIS in the studied population, the number of patients (as well as rate among the total population) showing a benefit of at least 20 percentage points in HINT-Q score after 6 months of device use when compared to baseline will be computed (table 8 with the related figure and table 16.6).

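### The conditional rule that drops the most deviant site selects on the outcome, so the re-estimated mean is biased when it fires; the damage is confined to a supportive estimate

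*SAP*

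**What the plan says.** SAP 6.5 and Protocol 3.6.2.4 h give the same procedure. Among English-speaking patients, the change from baseline to month 6 is analysed by ANOVA with site as the factor, and a forest plot of site means with 95% CIs is produced whatever the p value. A further step is conditional. When the ANOVA is significant and the sites also differ qualitatively, the instruction is that "the site with the largest mean deviation from the overall mean change from baseline will be removed from the sample", after which the mean change is estimated in the sites that remain.

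Three things are left open in both documents:
- what counts numerically as a qualitative difference;
- whether the deviation is absolute or signed;
- whether the removed site has to be the one pointing the other way.

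No data-quality, conduct or calibration reason is needed for removal.

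The status of the analysis is clear. The protocol places it among the secondary analyses and states: "All secondary or sensitivity analyses are supportive estimates of effects related to the primary or secondary objectives". It adds: "Claims for labeling will be based only on confirmatory results". For the primary test, SAP 6.1 says: "The primary analysis of the primary efficacy endpoint will be performed on a subgroup of the FAS which consists of all English-speaking subjects".

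**The concern.** A site leaves the sample because of its observed mean. Fixing the rule in advance does not cure this, since which site goes, and whether any goes, still depends on the outcome. The SAP states of HINT-Q: "An improvement of approximately 50 points with respect to baseline is expected". Against that background a site with an opposite result will normally be the low one, so the re-estimate tends to exceed the all-site mean. Neither document asks for an interval that allows for the selection, or for the corresponding result with each other site left out. A report could therefore set beside the primary result a second, higher mean with a conventional CI, and a reader could take it for the cleaner estimate. That would happen mainly when one site has truly done badly, which is when site results matter most.

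**Working it through.** **Inputs from the documents.** Expected change 50 points and clinically pertinent change 20 points (SAP 1.2); SD of change 25 and 39 English-speaking patients (SAP 1.3); default significance level 5% (SAP 3), since none is given for the site ANOVA.

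**Assumptions not in the documents.** 3 to 5 sites with English-speaking patients. Equal layouts: 13/13/13, 10/10/10/9, 8/8/8/8/7. Unequal layouts: 20/12/7, 17/11/7/4, 15/10/7/4/3. Qualitative means at least one site mean below 0 and one above 0. Deviation is absolute. Scores are normal, ignoring the 0 to 100 bounds.

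**The plan's own figure.** None is given for the site rule. The sample size built on the same mean and SD is consistent: exact one-sample t power at one-sided 0.025 is 90.9% for n = 5, 97.1% for n = 6 and 99.1% for n = 7, against the stated 7 for 95% power.

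**Arithmetic of removal.** If a site of size n_f with mean m_f is dropped from N patients and the rest have mean m_r, then

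shift = n_f × (m_r − m_f) / N.

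- Upward example: sizes 8/8/8/8/7, means 50/50/50/50/−5. All-site mean = (32 × 50 − 35)/39 = 40.1. The rule drops −5 and gives 50.0. Shift = 7 × 55/39 = +9.9.
- Downward example: same sizes, means −2/10/12/15/60. All-site mean = (280 + 420)/39 = 17.9. Deviations are −19.9 for the negative site and +42.1 for the best one, so the best site is dropped and the mean becomes 280/32 = 8.8. The negative site stays.

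**Simulation, one failing site, others at 50, within-site SD 25** (300,000 trials per layout; in unequal layouts the failing site is the smallest):

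| True change at failing site | Layout | Rule fires | Mean shift when it fires |
|---|---|---|---|
| 0 | equal, 3 / 4 / 5 sites | 50% / 50% / 50% | +18.5 / +13.1 / +10.3 |
| −10 | equal, 3 / 4 / 5 sites | 93% / 89% / 86% | +20.3 / +14.3 / +11.2 |
| 0 | unequal, 3 / 4 / 5 sites | 50% / 50% / 48% | +10.3 / +6.2 / +4.8 |
| −10 | unequal, 3 / 4 / 5 sites | 86% / 79% / 74% | +11.2 / +6.6 / +5.1 |

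The shift is upward in 99.9% to 100% of firings. The formula explains most of its size: with 10/10/10/9 and the 9-patient site at 0, 9 × 50/39 = 11.5. The simulated 13.1 is larger because firing also requires that site's observed mean to be below 0. In that layout the ordinary 95% CI from the remaining sites covers the true all-site mean (38.5 or 36.2) in only 17% to 32% of firings; coverage is better when the failing site is small.

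**Simulation, no planted failure, total SD 25** (1,000,000 trials per layout; all layouts pooled as ranges):

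| Overall mean | Between-site SD | Rule fires | Upward when it fires | Mean shift when it fires |
|---|---|---|---|---|
| 50 | 10 | 0.005% to 0.19% | 96% to 99% | +5 to +17 |
| 50 | 15 | 0.3% to 1.0% | 72% to 94% | +6 to +14 |
| 50 | 20 | 2% to 4% | 61% to 86% | +4 to +11 |
| 20 | 10 to 20 | 11% to 59% | 53% to 68% | +0.7 to +3.5 |

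At a true mean of 0 the direction is even and there is no net shift.

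**The case against.** The strongest reply is that little rests on this estimate. The confirmatory t-test uses all English-speaking FAS patients, the all-site mean is reported in SAP Table 8, and labeling claims rest on the primary analysis. That stands. A reader might infer that the headline effect could rise by 10 to 20 points; it cannot.

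A reader might also infer that a failing site would be hidden. The forest plot is mandatory whatever the ANOVA shows, so every site's mean and CI stay visible.

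The rule is written in advance, needs two conditions, and labels its result as the mean in the remaining sites. Read strictly that way, an estimate near 50 in the failing-site scenarios is right for those sites. This stands in part: the difficulty is that the sites it describes are picked by outcome, so it does not estimate the effect in the trial population.

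A site with a true mean change of −10 is an extreme case. The protocol cites baseline means of 11.3% and 14%, scores cannot fall below 0, and the normal model ignores that floor. The scenario with a true change of 0 depends less on this and still gives +10 to +18.5 points with equal sites.

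Finally, SAP 6.3.4 states: "All analyses performed on the HINT-Q will be replicated on the HINT-N". One might conclude that the rule would fire readily on HINT-N, where effects could be smaller. The documents do not settle this. Protocol 3.6.2.4 d takes change from baseline as the HINT-N response. SAP 6.3.4 takes the post-implantation score, which cannot be negative, so a trigger based on opposite signs could not fire. The HINT-N tables are not by site, the planned site forest plot is for HINT-Q, and no HINT-N effect size is given.

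**Conclusion.** The concern holds within limits. When the rule fires, the re-estimated mean is selected on the outcome and its ordinary CI takes no account of that. With one truly failing site at the planned effect, it overstates the all-site mean by about 10 to 20 points for equal sites, and by about 5 to 11 if the failing site is the smallest. With no failing site and little heterogeneity, firing is very rare.

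It would be too strong to say that the bias is almost always upward. That is true for a single failing site, or for modest heterogeneity around 50, but not under wide heterogeneity or a 20-point mean, where the rule may discard the best site and keep a negative one.

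The primary analysis is not affected. The figures depend on the assumed number and sizes of sites, the between-site SD, the sign-based reading of qualitative, and normal scores. The change is worth making because the estimate is misleading when it appears and the remedy is cheap.

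**What to change.** In SAP 6.5 and Protocol 3.6.2.4 h:
- Delete the sentence that removes a site.
- State that the mean over all English-speaking FAS patients remains the reported estimate whatever the site ANOVA shows.
- Report the mean change and 95% CI with each site left out in turn, for every site, beside the forest plot and regardless of the ANOVA p value. This still shows what the removal rule was meant to show, without choosing one result.
- If the term qualitative difference is kept to describe the forest plot, define it numerically.
- Treat a model with a random site effect as optional, because with at most five English-speaking sites its variance would be poorly estimated.

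In Protocol 3.6.2.4 d and SAP 6.3.4, use one definition of the HINT-N response and say whether the site analysis applies to it.

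The cost is wording in two documents and at most five extra table rows. No new data are needed, and neither the sample size nor the primary test changes.

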## 7. Mock of tables

**Table 1 : Disposition of patient**

	English speaking patients N=	French speaking patients N=	Danish speaking patients N=	Global population N=
Screening patients	xx	xx	xx	xx
Included patients	xx (xx.xx%)	xx (xx.xx%)	xx (xx.xx%)	xx (xx.xx%)
Surgery	xx (xx.xx%)	xx (xx.xx%)	xx (xx.xx%)	xx (xx.xx%)
Activation	xx (xx.xx%)	xx (xx.xx%)	xx (xx.xx%)	xx (xx.xx%)
Visit at M3	xx (xx.xx%)	xx (xx.xx%)	xx (xx.xx%)	xx (xx.xx%)
Visit at M6	xx (xx.xx%)	xx (xx.xx%)	xx (xx.xx%)	xx (xx.xx%)
Visit at M12	xx (xx.xx%)	xx (xx.xx%)	xx (xx.xx%)	xx (xx.xx%)
Full Analysis Set	xx (xx.xx%)	xx (xx.xx%)	xx (xx.xx%)	xx (xx.xx%)
Exclusion reason 1	xx (xx.xx%)	xx (xx.xx%)	xx (xx.xx%)	xx (xx.xx%)
Exclusion reason 2	xx (xx.xx%)	xx (xx.xx%)	xx (xx.xx%)	xx (xx.xx%)
...				
Per Protocol Set	xx (xx.xx%)	xx (xx.xx%)	xx (xx.xx%)	xx (xx.xx%)
Exclusion reason 1	xx (xx.xx%)	xx (xx.xx%)	xx (xx.xx%)	xx (xx.xx%)
Exclusion reason 2	xx (xx.xx%)	xx (xx.xx%)	xx (xx.xx%)	xx (xx.xx%)
...				
Safety Analysis Set	xx (xx.xx%)	xx (xx.xx%)	xx (xx.xx%)	xx (xx.xx%)
Exclusion reason 1	xx (xx.xx%)	xx (xx.xx%)	xx (xx.xx%)	xx (xx.xx%)
Exclusion reason 2	xx (xx.xx%)	xx (xx.xx%)	xx (xx.xx%)	xx (xx.xx%)
...				

**Table 2 : Discontinuation**

	English speaking patients N=	French speaking patients N=	Danish speaking patients N=	Global population N=
Discontinuation of study	x (xx.xx%)	x (xx.xx%)	x (xx.xx%)	x (xx.xx%)
Screen failure	x	x	x	x
Adverse event	x	x	x	x
Death	x	x	x	x
Patient request	x	x	x	x
Investigator decision	x	x	x	x
Loss to follow up	x	x	x	x
Protocol deviation	x	x	x	x
Study terminated by the sponsor	x	x	x	x
Other	x	x	x	x

**Table 3 : Demographics – SAS, FAS and PPS population**

	English speaking patients N=	French speaking patients N=	Danish speaking patients N=	Global population N=
Age (years)	x.xx±x.x CI= [x.x;x.x] [xx ; xx] Med=x Missing=x			
	[18; 40 [ [40; 50 [ [50; 60 [ >= 60	x (xx.xx%) x (xx.xx%) x (xx.xx%) x (xx.xx%)	x (xx.xx%) x (xx.xx%) x (xx.xx%) x (xx.xx%)	x (xx.xx%) x (xx.xx%) x (xx.xx%) x (xx.xx%)
Gender	Male Female	x (xx.xx%) x (xx.xx%)	x (xx.xx%) x (xx.xx%)	x (xx.xx%) x (xx.xx%)
BMI (kg/m  )	x.xx±x.x CI= [x.x;x.x] [xx ; xx] Med=x Missing=x			
	[18; 25 [ [25; 30 [ [30; 35 [ >= 35	x (xx.xx%) x (xx.xx%) x (xx.xx%) x (xx.xx%)	x (xx.xx%) x (xx.xx%) x (xx.xx%) x (xx.xx%)	x (xx.xx%) x (xx.xx%) x (xx.xx%) x (xx.xx%)

**Table 4 : Medical history – SAS, FAS and PPS population**

		English speaking patients N=	French speaking patients N=	Danish speaking patients N=	Global population N=
Allergies	Yes	x (xx.xx%)	x (xx.xx%)	x (xx.xx%)	x (xx.xx%)
	No	x (xx.xx%)	x (xx.xx%)	x (xx.xx%)	x (xx.xx%)
Significant medical history	Yes	x (xx.xx%)	x (xx.xx%)	x (xx.xx%)	x (xx.xx%)
	No	x (xx.xx%)	x (xx.xx%)	x (xx.xx%)	x (xx.xx%)
Significant concomitant disease	Yes	x (xx.xx%)	x (xx.xx%)	x (xx.xx%)	x (xx.xx%)
	No	x (xx.xx%)	x (xx.xx%)	x (xx.xx%)	x (xx.xx%)
Concomitant medication	Yes	x (xx.xx%)	x (xx.xx%)	x (xx.xx%)	x (xx.xx%)
	No	x (xx.xx%)	x (xx.xx%)	x (xx.xx%)	x (xx.xx%)

**Table 5 : Hearing history – SAS, FAS and PPS population**

	English speaking patients N=	French speaking patients N=	Danish speaking patients N=	Global population N=
Etiology				
For right ear				
Aging	x (xx.xx%)	x (xx.xx%)	x (xx.xx%)	x (xx.xx%)
Auto immune	x (xx.xx%)	x (xx.xx%)	x (xx.xx%)	x (xx.xx%)
Genetics	x (xx.xx%)	x (xx.xx%)	x (xx.xx%)	x (xx.xx%)
Noise exposure	x (xx.xx%)	x (xx.xx%)	x (xx.xx%)	x (xx.xx%)
Ostosclerosis	x (xx.xx%)	x (xx.xx%)	x (xx.xx%)	x (xx.xx%)
Meniere's disease	x (xx.xx%)	x (xx.xx%)	x (xx.xx%)	x (xx.xx%)
Acoustic neuroma	x (xx.xx%)	x (xx.xx%)	x (xx.xx%)	x (xx.xx%)
Meningitis	x (xx.xx%)	x (xx.xx%)	x (xx.xx%)	x (xx.xx%)
...				
For left ear				
Aging	x (xx.xx%)	x (xx.xx%)	x (xx.xx%)	x (xx.xx%)
Auto immune	x (xx.xx%)	x (xx.xx%)	x (xx.xx%)	x (xx.xx%)
Genetics	x (xx.xx%)	x (xx.xx%)	x (xx.xx%)	x (xx.xx%)
Noise exposure	x (xx.xx%)	x (xx.xx%)	x (xx.xx%)	x (xx.xx%)
Ostosclerosis	x (xx.xx%)	x (xx.xx%)	x (xx.xx%)	x (xx.xx%)
Meniere's disease	x (xx.xx%)	x (xx.xx%)	x (xx.xx%)	x (xx.xx%)
Acoustic neuroma	x (xx.xx%)	x (xx.xx%)	x (xx.xx%)	x (xx.xx%)
Meningitis	x (xx.xx%)	x (xx.xx%)	x (xx.xx%)	x (xx.xx%)
...				
Duration of hearing loss (years)				
Right ear	x.xx±x.x CI= [x.x;x.x] [xx ; xx] Med=x Missing=x			
Left ear	x.xx±x.x CI= [x.x;x.x] [xx ; xx] Med=x Missing=x			
Duration of first used hearing aid (years)				
Right ear	x.xx±x.x CI= [x.x;x.x] [xx ; xx] Med=x Missing=x			
Left ear	x.xx±x.x CI= [x.x;x.x] [xx ; xx] Med=x Missing=x			

	English speaking patients N=	French speaking patients N=	Danish speaking patients N=	Global population N=
Duration of severe to profound hearing loss (years) Right ear	x.xx±x.x CI= [x.x;x.x] [xx ; xx] Med=x Missing=x			
Left ear	x.xx±x.x CI= [x.x;x.x] [xx ; xx] Med=x Missing=x			
Vertigo	Yes No	x (xx.xx%) x (xx.xx%)	x (xx.xx%) x (xx.xx%)	x (xx.xx%) x (xx.xx%)
Tinnitus	Yes No	x (xx.xx%) x (xx.xx%)	x (xx.xx%) x (xx.xx%)	x (xx.xx%) x (xx.xx%)
CT imaging bony labyrinth cochlear malformation ossification	x (xx.xx%) x (xx.xx%) x (xx.xx%) x (xx.xx%)			
MRI auditory nerve lesions cochlear malformation ossification, fibrosis central lesions of the auditory pathway	x (xx.xx%) x (xx.xx%) x (xx.xx%) x (xx.xx%) x (xx.xx%)			
Audiological assessment				
Pure tone audiometry (days) right 250Hz	x.xx±x.x CI= [x.x;x.x] [xx ; xx] Med=x			
500Hz	x.xx±x.x CI= [x.x;x.x] [xx ; xx] Med=x			
1kHz	x.xx±x.x CI= [x.x;x.x] [xx ; xx] Med=x			
2kHz	x.xx±x.x	x.xx±x.x	x.xx±x.x	x.xx±x.x

		CI= [x.x;x.x] [xx ; xx] Med=x			
4kHz		x.xx±x.x CI= [x.x;x.x] [xx ; xx] Med=x			
8kHz		x.xx±x.x CI= [x.x;x.x] [xx ; xx] Med=x			
left	250Hz	x.xx±x.x CI= [x.x;x.x] [xx ; xx] Med=x			
	500Hz	x.xx±x.x CI= [x.x;x.x] [xx ; xx] Med=x			
	1kHz	x.xx±x.x CI= [x.x;x.x] [xx ; xx] Med=x			
	2kHz	x.xx±x.x CI= [x.x;x.x] [xx ; xx] Med=x			
	4kHz	x.xx±x.x CI= [x.x;x.x] [xx ; xx] Med=x			
	8kHz	x.xx±x.x CI= [x.x;x.x] [xx ; xx] Med=x			
Performance of Tympanometry		x (xx.xx%)	x (xx.xx%)	x (xx.xx%)	x (xx.xx%)
Yes*		x (xx.xx%)	x (xx.xx%)	x (xx.xx%)	x (xx.xx%)
No					
*If yes, results for right ear					

		Ear Canal Volume	x.xx±x.x CI= [x.x;x.x] [xx ; xx] Med=x				
		daPa	x.xx±x.x CI= [x.x;x.x] [xx ; xx] Med=x				
		Compliance	x.xx±x.x CI= [x.x;x.x] [xx ; xx] Med=x				
*If yes, results for left ear		Ear Canal Volume	x.xx±x.x CI= [x.x;x.x] [xx ; xx] Med=x				
		daPa	x.xx±x.x CI= [x.x;x.x] [xx ; xx] Med=x				
		Compliance	x.xx±x.x CI= [x.x;x.x] [xx ; xx] Med=x				
Speech perception test		Yes	x (xx.xx%)	x (xx.xx%)	x (xx.xx%)	x (xx.xx%)	
		No	x (xx.xx%)	x (xx.xx%)	x (xx.xx%)	x (xx.xx%)	
Performance of Speech audiometry routine test		Yes**	x (xx.xx%)	x (xx.xx%)	x (xx.xx%)	x (xx.xx%)	
		No	x (xx.xx%)	x (xx.xx%)	x (xx.xx%)	x (xx.xx%)	

\*\*if yes, results by patient will be presented through a listing.

**Table 6 : Time between visits – SAS, FAS and PPS population**

Time between visits	English speaking patients N=	French speaking patients N=	Danish speaking patients N=	Global population N=
Time between surgery and inclusion (days)	x.xx±x.x CI= [x.x;x.x] [xx ; xx] Med=x Missing=x			
Time between activation and surgery (days)	x.xx±x.x CI= [x.x;x.x] [xx ; xx] Med=x Missing=x			
Time between Fu V4 and surgery (months)	x.xx±x.x CI= [x.x;x.x] [xx ; xx] Med=x Missing=x			
Time between Fu V6 and surgery (months)	x.xx±x.x CI= [x.x;x.x] [xx ; xx] Med=x Missing=x			
Time between Fu V7 and surgery (months)	x.xx±x.x CI= [x.x;x.x] [xx ; xx] Med=x Missing=x			
Time between Fu V8 and surgery (months)	x.xx±x.x CI= [x.x;x.x] [xx ; xx] Med=x Missing=x			
Time between End of study and surgery (months)	x.xx±x.x CI= [x.x;x.x] [xx ; xx] Med=x Missing=x			
Time between unscheduled visit and surgery (months)	x.xx±x.x CI= [x.x;x.x] [xx ; xx] Med=x Missing=x			

